
**15.6.3. Efficacy**

[figure not shown]
Hgb Values
Central Laboratory and HemoCue Hgb Values

 
• For reporting purposes, central laboratory Hgb values will be used, unless otherwise specified. However, if a central laboratory Hgb value is missing, a corresponding non-missing HemoCue Hgb value, which is associated with the identical subject number and visit, will be used.
 

Evaluable Hgb Values

 
• It will be used for reporting sensitivity analysis results and Hgb listings.
 
• Evaluable Hgb values will be based on on-therapy central laboratory and/or HemoCue Hgb values that are not taken within the 8 weeks following a transfusion or within the 8 weeks following a non-
 

**Hgb Values**

randomized ESA medication (except protocol-specified ESA treatment in screening period).  
If an Hgb record meets at least one following criteria, the Hgb record will be regarded as non-evaluable.

- Blood Product Administration Date < Date ≤ Blood Product Administration Date + 56 (days)
- ESA Start Date < Date of Hgb data ≤ ESA Stop Date + 56 (days)

**Flowchart for Hgb Analyses**

- This flowchart will be applicable, unless otherwise specified
  - Basically, scheduled visits between Day 1 and Week 52 will be applicable to this flowchart, but analyses including by-visit summaries may include other scheduled visits (ie. screening and follow-up visit).
- [1] Regarding partially evaluated Hgb values, the following summaries of Hgb will include unscheduled visits:
- Summary of Time (weeks and %) within Hgb target range during the primary efficacy evaluation period
  - Summary of Number (%) of subjects who have an Hgb level of less than 7.5 g/dL
  - Summary of Number (%) of subjects who have an Hgb level of more than 13.0 g/dL and number of episodes

**Hgb Increase of More than 2.0 g/dL over Any 4 Weeks**

- For this reporting purpose, Hgb values from central laboratory will be used as previously described.
- A subject who has at least one record with Hgb increase of more than 2.0 g/dL over any 4 weeks will be counted and all episodes will be listed.
- Hgb increase will be calculated for scheduled visits between Day 1 and Week 52 if available (i.e. Week 4 Hgb - Day 1 Hgb, Week 8 Hgb - Week 4 Hgb, ...)

Illustration of calculation (example in case of Week 12 missing, until Week 24 visit)

Hgb (g/dL)	Lab Date	Study Day	Visit	Hgb increase
9.1	01FEB2017	1	Day 1	Not calculated
9.8	02MAR2017	30	Week 4	0.7
11.9	02APR2017	61	Week 8	2.1
12.6	07JUN2017	127	Week 16	Not calculated
12.7	08JUL2017	158	Week 20	0.1
12.3	02AUG2017	183	Week 24	-0.4

- Odds ratio and its 95% CI will be obtained using the same statistical model described in Section 7.2.5.
- When the odds ratio is undefined, it will not be presented.

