4.5. Rationale for Dose Levels

Starting dose and dose adjustments of daprodustat

The starting dose (4 mg) and the dose adjustment method (maintenance dose range: 1-24 mg) for daprodustat are described in Section 6.4.

The starting dose and the dose adjustment algorithm selected for Japanese HD subjects in the present study are based on the results from a review of the longitudinal model constructed using Hgb data from six Japanese or overseas Phase II studies (PHI112844, PHI116581, PHI116582, PHI113633, PHI113747, and PHI116099) as well as the results from clinical studies. The data set used in the model analyses was based on the data of daprodustat administered in a wide dose range (0-25 mg) and included a Japanese Phase II 4-week treatment study (PHI116099) and international multi-center late Phase II 24-week treatment studies (PHI113633 and PHI113747) in which subjects in Japan participated.

Starting dose

Simulations using a longitudinal model as well as clinical data for HD subjects suggested that Hgb levels observed with prior ESA therapy is maintained for 4 weeks after a switch from prior ESA to study medication, with no rapid increase greater than 2 g/dL, at the dose level of 4 mg in ESA user subjects. Covariate analyses identified baseline Hgb, body weight, and dose level of prior ESA as major factors affecting Hgb. However, Hgb was more greatly affected by inter-subject differences in drug response to daprodustat than these factors.

Taken together, 4 mg may be an appropriate starting dose of daprodustat for the majority of ESA users.

Maintenance dose range and dose adjustment algorithm

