9.4.3. Other Secondary Efficacy Analyses

Among the secondary efficacy endpoints, the time (%) in Hgb target range during the primary efficacy evaluation period , and proportion of subjects who have an Hgb increase of more than 2 g/dL over any 4 weeks, the point estimates and 95% CIs for the treatment difference (or odds ratio) in HD subjects will be calculated. Other secondary efficacy and exploratory endpoints will be summarized by each treatment group.

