#### 7.2.5.1. Statistical Methodology Specification

Endpoint / Variables

 
Number (%) of subjects with mean Hgb in the target range (10.0-12.0 g/dL) during the primary efficacy evaluation period (Week 40 to 52)
 

Model Specification

 
The percentage of subjects with observed mean Hgb during the primary efficacy evaluation period within the target range will be derived from the average of observed Hgb values during the primary efficacy evaluation period for individuals.
 
Analyses will be conducted by a logistic regression model as follows: <math display="block">\text{logit}(\pi) = \beta_0 + \beta_{\text{baseline}} * \text{Baseline}_i + \beta_j + \varepsilon</math> 
 <math>\pi_i</math>: treatment success (mean(Hgbi) is within the target range or not)  <math>\beta_0</math>: Intercept  <math>\beta_{\text{baseline}}</math>: baseline Hgb effect  <math>\text{Baseline}_i</math>: Hgb measurement for subject i  <math>\beta_j</math>: treatment effect (j= daprodustat, darbepoetin alfa)  <math>\varepsilon</math>: random error  i: subject (i = 1, 2, ..., N) 
 
 

N: number of subjects included in the analysis

- The mean Hgb during the primary efficacy evaluation period will be calculated for each individual and confirmed if the values are in the target range or not. Therefore, subjects who have at least one Hgb measurement during the evaluation period will be included in this analysis. A subject who has missing data of the mean Hgb during the primary evaluation period due to intercurrent events will be regarded as a non-responder.
- The odds ratio (daprodustat/darbepoetin alfa) will be obtained as follows:  

$$OR = \exp(\beta_{\text{daprodustat}} - \beta_{\text{darbepoetin alfa}})$$
 The odds ratio, the Wald-type 95% CI and a superiority one-sided p-value based on a z-score will be provided together.

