### Model Checking & Diagnostics

- If the logistic regression cannot be applicable due to all responders or all non-responders, the odds ratio and the associated statistics will not be provided.

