The number and percentage of subjects who have an Hgb increase of more than 2.0 g/dL over any 4 weeks during the treatment period will be summarized by treatment group. The odds ratio (daprodustat/darbepoetin alfa) will also be provided with its 95% CI. On-therapy Hgb values will be used for the summary. See Section 15.6.3 for details.

Number (%) of subjects who have an Hgb level of more than 13.0 g/dL and number of episodes

The number and percentage of subjects who have an Hgb level of more than 13.0 g/dL during the treatment period and number of episodes will be summarized by treatment group. On-therapy Hgb values observed in both scheduled and unscheduled visits will be included in the summary.

Scatter plot of Hgb assessments: Central Laboratory vs. HemoCue

A scatter plot of Hgb values measured by Central Laboratory versus Hgb values measured by Hemocue will be produced along with Pearson's correlation coefficient. Regardless of visit and treatment group, all available pairs of Hgb (i.e. non-missing values in both from central laboratory and from the corresponding HemoCue measurement) will be used.

- **Dose adjustment**

The dose adjustment algorithm is described in Section 15.6.3, based on HemoCue Hgb values.

Dose at each assessment visit/ final visit

Dose at each assessment visit and final visit will be summarized using mean, standard deviation, minimum, P25, median, P75, mode, and maximum at each assessment visit by treatment. The final visit will be the last visit of treatment exposure for each subject.

Mean dose during Week 40 to 52 will also be summarized and includes subjects who has at least one exposure record during Week 40 to 52. This will also be summarized by prior ESA type, prior ESA dose, and ERI subgroup.

Number (%) of subjects with each dose at each assessment visit

The number and percentage of subjects with each dose (mg or µg) will be provided by treatment. Graphical summaries of histogram will be provided with the number of subjects in each dose by treatment. Dose categories will be classified into 10; N/A (not administered), 0 mg (treatment interruption), 1 mg, 2 mg, 4 mg, 6 mg, 8 mg, 12 mg, 18 mg, and 24 mg for daprodustat and classified into 9; N/A, 0 µg, 10 µg, 15 µg, 20 µg, 30 µg, 40 µg, 60 µg for darbepoetin alfa. This will also be summarized by prior ESA type, prior ESA dose, and ERI subgroup.

Duration (days) of treatment interruption due to Hgb >13.0 g/dL - daprodustat

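### Hgb rise of more than 2.0 g/dL over 4 weeks: the only planned between-arm estimate is an odds ratio withheld when undefined, with nothing in its place

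*SAP*

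**What the plan says.** Protocol 9.4.3 singles out two of the other secondary efficacy endpoints for estimation: time in the Hgb target range, and the proportion with an Hgb rise above 2 g/dL over any 4 weeks. For these, "the point estimates and 95% CIs for the treatment difference (or odds ratio) in HD subjects will be calculated". The remaining ones are only summarized by group.

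For the rapid-rise endpoint, SAP 7.3.2 gives the number and percentage of subjects by arm and one contrast: "The odds ratio (daprodustat/darbepoetin alfa) will also be provided with its 95% CI". SAP 15.6.3 names the model: "Odds ratio and its 95% CI will be obtained using the same statistical model described in Section 7.2.5". That is a logistic regression on treatment and baseline Hgb, for which SAP 7.2.5.1 specifies "The odds ratio, the Wald-type 95% CI and a superiority one-sided p-value based on a z-score will be provided together". SAP 15.6.3 ends with the rule "When the odds ratio is undefined, it will not be presented".

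The referenced model carries a similar rule: "If the logistic regression cannot be applicable due to all responders or all non-responders, the odds ratio and the associated statistics will not be provided". Neither place names a substitute estimate. For time in target range, SAP 7.3.2 does plan a treatment difference with a 95% CI.

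**The concern.** The protocol accepts either of two measures. The SAP chose the one that may not exist for some data sets and planned nothing for that case. A difference in proportions exists whatever the counts are.

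If one arm has no events, the commitment in protocol 9.4.3 goes unmet. Whether a between-arm estimate appears then depends on the observed result, and any estimate added later would be post hoc. What is at stake is one estimate and its interval for a secondary endpoint that bears on Hgb control. No confirmatory conclusion is involved.

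**Working it through.** **Inputs.** From the documents: 135 subjects randomized per arm (protocol 9.2.1); a logistic model with treatment and baseline Hgb and a Wald interval (SAP 7.2.5.1); ITT population (SAP 7.3.3). The plan states no figure for this endpoint, so there is none to reproduce. Assumptions: all 135 per arm are analyzed, the true event rate p is the same in both arms, and p runs from 0.5% to 5%. The baseline Hgb values in the model fits of step 1 are simulated.

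**Step 1: does the odds ratio fail with a zero-event arm?** Fitting the planned model by maximum likelihood to 0/135 against 10/135, the log odds ratio keeps moving as iterations are added:

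| Iterations | Log odds ratio | Standard error |
|---|---|---|
| 8 | -7.1 | 6.2 |
| 25 | -24.1 | about 30,000 |
| 35 | -34.1 | about 4.4 million |

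The estimate runs off to an odds ratio of 0 (or to infinity if darbepoetin alfa is the arm without events). A Wald interval built on it carries no information. Whether the result is withheld or printed, no usable estimate remains.

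**Step 2: how often would this happen?** The chance that a given arm has no events is q = (1 - p)^135. The chance that exactly one arm has none is 2q(1 - q).

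| Assumed p, both arms | q | Exactly one arm with no events |
|---|---|---|
| 0.5% | 0.508 | 50% |
| 1% | 0.257 | 38% |
| 2% | 0.065 | 12% |
| 3% | 0.016 | 3% |
| 5% | 0.001 | 0.2% |

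With unequal rates, the chance for the lower-rate arm is still q at its own rate. At 1% against 5% it is 0.99^135 = 26%, so a true difference does not prevent the failure.

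**Step 3: would such results be clear?** Two-sided Fisher p-values for no events against x events, 135 per arm: x = 5, 0.060; x = 6, 0.030; x = 10, 0.002. About six events in the other arm are needed to pass 5%. Under equal rates, the chance of no events in one arm and six or more in the other is 2q × P(X ≥ 6), with X binomial(135, p). This is 0.13% at p = 1% and 0.7% at p = 2%. As a share of the one-zero-arm outcomes, that is about 0.3% (0.13/38) and 5.9% (0.7/12).

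**Step 4: what would a risk difference give?** Percentage points, zero-event arm minus the other, 135 per arm:

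| Events in the other arm | Difference | Newcombe 95% CI | Miettinen-Nurminen 95% CI |
|---|---|---|---|
| 1 | -0.7 | -4.1 to 2.1 | -4.1 to 2.1 |
| 5 | -3.7 | -8.4 to -0.2 | -8.4 to -0.9 |
| 6 | -4.4 | -9.4 to -0.8 | -9.4 to -1.6 |
| 10 | -7.4 | -13.1 to -3.1 | -13.1 to -4.1 |

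An estimate and interval exist in every row. A Firth-penalized odds ratio is finite too: 0.09 (Wald 95% CI 0.005 to 1.42) at five events and 0.04 (0.003 to 0.67) at ten.

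**The case against.** The strongest reply is that the failure may never arise. The documents give no rate over 52 weeks, and the endpoint has many chances to occur: up to 13 consecutive 4-week intervals per subject between Day 1 and Week 52, in both arms, under dose titration. The daprodustat dose-adjustment table (protocol 6.4.1.2) has two rows triggered by a rise above 2.0 g/dL, so the protocol provides for such rises. At rates of 3% or more in both arms the problem nearly vanishes. This stands, and it limits the size of the point.

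It also blocks a tempting inference, that the protocol itself expects the event to be rare. Protocol 4.5 says that Hgb would be held after the switch "with no rapid increase greater than 2 g/dL, at the dose level of 4 mg in ESA user subjects". That statement concerns the first 4 weeks on one fixed dose of daprodustat. It says nothing about the later weeks or about darbepoetin alfa.

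A reader might also infer that a zero-event arm is the clearest possible result, so that the rule removes the strongest evidence. Step 3 does not support this. With fewer than about six events in the other arm the comparison is not clear, and at low equal rates nearly all one-zero-arm outcomes are of that kind.

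Three further replies have weight. Counts and percentages by arm are always reported and the episodes are listed, so a reader can work out a difference. Choosing the odds ratio complies with the protocol, which offers either measure. The endpoint is compared without multiplicity adjustment, on a complementary or exploratory basis (protocol 9.3.3). Finally, the SAP does not define when an odds ratio is undefined, and its phrase about all responders or all non-responders could mean one arm or all subjects pooled. A zero-event arm is the natural reading but not a certain one.

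These replies reduce the impact. None of them supplies the estimate and interval that protocol 9.4.3 says will be calculated.

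**Conclusion.** The point holds as a minor gap. The SAP narrows the protocol's choice of measures to one that fails when an arm has no events, states that it will then be omitted, and names no substitute. Under the equal-rate assumption with 135 per arm, this is a real possibility at true rates of about 2% or lower and a remote one at 5%. The documents do not show where in that range the trial lies.

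They do not support a claim that decisive evidence would be concealed, or that the odds ratio departs from the protocol. What would be lost is a planned between-arm estimate with its interval. The primary and principal secondary conclusions are unaffected.

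**What to change.** In SAP 7.3.2, SAP 15.6.3 and Table 2.23:

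- Report the difference in proportions (daprodustat minus darbepoetin alfa) with a Miettinen-Nurminen or Newcombe 95% CI in all cases, beside the existing odds ratio. Choose one interval method in advance.
- Replace the sentence "When the odds ratio is undefined, it will not be presented" with a rule that defines the case: when either arm has no events, or events in every subject, the odds ratio is shown as not calculated, or is estimated by a named Firth or exact method, and the risk difference and its interval are still reported.

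The odds ratio need not lose its place as the planned contrast. Protocol 9.4.3 already allows a treatment difference, so an SAP change appears to be enough. The cost is a few lines of text, one more line in the table, and an unadjusted difference standing next to a baseline-adjusted odds ratio, which a footnote should point out.

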**Scatter Plot of Hgb Assessments: Central Laboratory vs. HemoCue**

- All available pairs of Hgb (i.e. non-missing values in both from central laboratory and from the

Hgb Values
corresponding HemoCue measurement) will be used, regardless of treatment groups and visits. The figure will include a linear regression line with 95% CI band, R-squared, and Pearson’s correlation coefficient.
Scatter Plot of Change from Baseline in Hgb at Week 4 vs. Covariates of Interest

 
The following scatter plot figures will be produced for overall:                             
 
Change from Baseline in Hgb at Week 4 vs. Body Weight at Screening
 
Change from Baseline in Hgb at Week 4 vs. Baseline Hgb
 
Change from Baseline in Hgb at Week 4 vs. Prior ESA Dose
 
 
 
Vertical axis will indicate the change from baseline in Hgb (g/dL) at Week 4, horizontal axis will indicate the covariates of interest; dry body weight (kg) at screening, baseline Hgb (g/dL), or prior ESA dose (IU/week).
 
Only individual plots will be provided unlike the scatter plot of Hgb assessments.
 

Scatter Plot of Mean Dose During Week 40 to 52 vs. Covariates of Interest

 
The following scatter plot figures will be produced for overall:                             
 
Mean Dose during Week 40 to 52 vs. Body Weight at Screening
 
Mean Dose during Week 40 to 52 vs. Baseline Hgb
 
Mean Dose during Week 40 to 52 vs. Prior ESA dose
 
 
 
Vertical axis will indicate the mean dose (mg), horizontal axis will indicate the covariates of interest; dry body weight (kg) at screening, baseline Hgb (g/dL), or prior ESA dose (IU/week).
 
Mean dose will be calculated from the arithmetic mean using the latest 3 exposure records (i.e., for completers Week 40, 44, and 48), which are based on the actual doses and the scheduled visits.
 
Subjects who has less than 3 dosing records will be excluded from the figures.
 
Mean dose during Week 40 to 52 will also be summarized and listed.
 
Only individual plots will be provided unlike the scatter plot of Hgb assessments.
 

Time in Target Range																												
Time (weeks and percentage) in Target Range During the Primary Efficacy Evaluation Period																												

 
For this reporting purpose, on-therapy Hgb values of central laboratory during Week 40 to Week 52, including unscheduled visits, will be used. However, if a central laboratory Hgb value is missing, a corresponding non-missing HemoCue Hgb value, which is associated with the identical subject number and visit, will be used.
 
Number of days that a subject’s Hgb is within the analysis range of 10.0-12.0 g/dL inclusive between Week 40 and 52, including any on-therapy Hgb values that were taken during this time period. Linear interpolation is used to estimate Hgb between visits, if a subject has an intermittent missing value (Rosendaal, 1993).
 
 
Illustration of calculation
 
  
 Hgb (g/dL)	Lab Date	Visit	Ref Day	Hgb Shift	Total shift (%) within range	Time in range (weeks)	
   
 9.9	01AUG2017	Week 40	0	NC	NC	NC	
 
 10.8	01SEP2017	Week 44	31	0.9 (=10.8-9.9)	total shift: 0.8 0.8/0.9=88.89%	(31-0)*0.8889/7 =27.56/7 (weeks)	
 
 missing	01OCT2017	Week 48	61	NA	NA	NC	
  
	Hgb (g/dL)	Lab Date	Visit	Ref Day	Hgb Shift	Total shift (%) within range	Time in range (weeks)	9.9	01AUG2017	Week 40	0	NC	NC	NC	10.8	01SEP2017	Week 44	31	0.9 (=10.8-9.9)	total shift: 0.8 0.8/0.9=88.89%	(31-0)*0.8889/7 =27.56/7 (weeks)	missing	01OCT2017	Week 48	61	NA	NA	NC
Hgb (g/dL)	Lab Date	Visit	Ref Day	Hgb Shift	Total shift (%) within range	Time in range (weeks)																						
9.9	01AUG2017	Week 40	0	NC	NC	NC																						
10.8	01SEP2017	Week 44	31	0.9 (=10.8-9.9)	total shift: 0.8 0.8/0.9=88.89%	(31-0)*0.8889/7 =27.56/7 (weeks)																						
missing	01OCT2017	Week 48	61	NA	NA	NC																						

Time in Target Range						
12.4	01NOV2017	Week 52	92	1.6 (=12.4-10.8)	total shift: 1.2 1.2/1.6=75%	(92-31)*0.75/7 =45.75/7 (weeks)
Overall time in the target range = (27.56 + 45.75)/7 = 73.31/7 = 10.47 (weeks)						
Percent time in the target range = 10.47/(92/7) = 79.68%						
NC: Not calculated, NA: Not available						

 
Hgb laboratory assessment date will be used to calculate a duration (Ref Day) between assessments.                             
 
Duration between assessments = [Hgb lab date] – [Hgb lab date of the previous measurement]
 
 
 
 
If a subject was withdrawn from the treatment before Week 40 so that the duration between Week 40 to Week 52 cannot be calculated, the subject will not be included in a summary.
 
Basically, the duration should be [Week 52 lab date – Week 40 lab date] unless a subject was withdrawn before Week 52. In this case, treatment stop date will be used instead of Week 52.
 
 
As an above example, suppose a subject has Hgb reading 9.9 g/dL on August 1st (Week 40), then reading if 10.8 g/dL on September 1st. The assumption is made that the week, between these scheduled assessments the subjects Hgb increases from 9.9 to 10.8 g/dL in a linear manner. The following steps are taken to calculate the time (days) the subject's Hgb was within target range (10.0 to 12.0 g/dL).                             
 
Calculate amount of Hgb shift (9.9 to 10.8 = 0.9 shift) and Hgb shift within range (0.8 out of shift is within range of 10.0 – 12.0)
 
Calculate percent of total shift (%) within range (0.8/0.9 = 88.89%)
 
Estimate the number of weeks since last visit within range (88.89% x duration between assessments = 88.89% x 31/7 weeks = 3.94 weeks within range)
 
 
 
 
If a subject has an intermittent missing Hgb assessment (on-therapy), the linear interpolation will be done by ignoring missing Hgb data.
 
To calculate overall time (weeks) in Hgb target range, the total days in range for each time period are added together and divided by 7.
 
The % of time in range between Week 40 and Week 52 for a subject will be calculated by calculating overall time (weeks) within range and dividing by the total duration (weeks) between Week 40 to Week 52. Similarly, the % of time above Hgb target range and % of time above and below Hgb target range will be calculated,
						

Dose Adjustment
Dose Adjustment Algorithm

 
Note that dose adjustment summaries will be produced only for daprodustat group.
 
Dose adjustment algorithm will be based on HemoCue Hgb values at scheduled visits. No Hgb values measured at unscheduled visits will be included.
 
Dose will be derived from actual dose associated with container numbers.
 
The following table illustrates the algorithm using analysis flags as below:                             
 
(FL_A): Adjustment flags will be counted if actual dose is changed from that of the previous visit.
 
(FL_B): Over 13.0 g/dL flags will be counted if HemoCue Hgb >13.0 g/dL is observed.
 
(FL_C): Interruption flags will be counted if actual dose is zero.
 
 
 
 
Treatment durations will be calculated based on the following formula:
 
 
Duration (days) = Treatment Stop Date – Treatment Start Date + 1 day
 

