6.4.1.1. Starting Dose

At Day 1, subjects will skip ESA and will start oral treatment with daprodustat at the starting dose of 4 mg once daily and remain on the same regimen until the day of Week 4.

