6.4.1.2. Maintenance Dose

From Weeks 4 to 52, interruption of treatment or dose adjustments will be made within the maintenance dose range of 1-24 mg (Table 5) according to the dose adjustment algorithm (Table 6) to achieve and/or maintain Hgb within the target range (10.0-12.0 g/dL) based on the HemoCue Hgb value measured every 4 weeks. Dose changes will be made every 4 weeks. If any of the one-step dose reduction criteria is met during treatment at the minimum maintenance dose (1 mg), treatment should be interrupted (and administer placebo); once the one-step dose increase criteria are met, treatment at 1 mg will be resumed. If the one-step dose increase criterion is met during treatment at the maximum maintenance dose (24 mg), treatment at 24 mg should be continued.

Table 5 Maintenance dose of daprodustat

Dose step	1	2	3	4	5	6	7	8
Dose level of	1 mg	2 mg	4 mg	6 mg	8 mg	12 mg	18 mg	24 mg
daprodustat								
(once daily)								
Number of	1 mg	2 mg	4 mg	6 mg	4 mg	6 mg	6 mg	6 mg
daprodustat	tablet	tablet	tablet	tablet	tablet	tablet	tablet	tablet
tablets taken	×1	×1	×1	×1	$\times 2$	×2	×3	×4

	,	, ,							
Hgb	Hgb increase over 4 weeks	Treatment							
(g/dL)	(g/dL)	Treatment							
>13.0	NA	Interrupt treatment (and administer placebo) until Hgb decreases to less than 12.0 g/dL, and resume treatment at the one lower dose level [If interrupted (and placebo administered) at 1 mg,							
		resume treatment at 1 mg after the one-step dose increase criterion is met]							
\geq 12.0 and \leq 13.0	NA	One-step dose reduction							
≥10.0 and <12.0	>2.0	One-step dose reduction							
	≤2.0	Continue treatment at the current dose level							
≥7.5 and <10.0	>2.0	One-step dose reduction							
	0.5-2.0	Continue treatment at the current dose level							
	<0.5	One-step dose increase							

Table 6 Dose adjustment algorithm (daprodustat)

NA

Discontinue treatment permanently* and initiate

another appropriate treatment

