Treatment differences (daprodustat – darbepoetin alfa) and the associated 95% CIs for change from baseline will be provided at each assessment (See Section 7.4.5.1). For ferritin, serum iron, and TIBC change from baseline, graphical summaries will be provided by treatment group using the adjusted means and the associated 95% CIs over time. For TSAT and hepcidin percent change from baseline, graphical summaries will be provided using adjusted geometric means percent change from baseline and the associated 95% CIs over time. These will also be summarized by baseline iron group.

- **Other**

Scatter plot of change from baseline in Hgb at Week 4 vs. covariates of interest

Scatter plot of change from baseline in Hgb at Week 4 versus following covariates of interest, body weight, baseline Hgb, prior ESA dose will be produced only for daprodustat. See Section 15.6.3 for the detailed derivations.

Scatter plot of mean dose during Week 40 to 52 vs. covariates of interest

Scatter plot of mean dose during Week 40 to 52 versus following covariates of interest, body weight, baseline Hgb, prior ESA dose will be produced only for daprodustat. See Section 15.6.3 for the detailed derivations.

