**7.4.3. Population of Interest**

The exploratory efficacy analyses will be based on the ITT population, unless otherwise specified.

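### The SAP's mean dose for Weeks 40 to 52 averages each subject's latest three records, so the daprodustat scatter plots include doses from before Week 40

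*SAP*

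**What the plan says.** SAP 15.6.3, in the entry on scatter plots of mean dose during Weeks 40 to 52, gives the derivation: "Mean dose will be calculated from the arithmetic mean using the latest 3 exposure records (i.e., for completers Week 40, 44, and 48". Doses are actual doses at scheduled visits. The only exclusion is "Subjects who has less than 3 dosing records will be excluded from the figures". The same entry adds that this mean dose is also summarized and listed, with no further condition.

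SAP 7.4.2 plans these plots for daprodustat only, against body weight, baseline Hgb and prior ESA dose, and refers to this derivation: "See Section 15.6.3 for the detailed derivations". On the population, SAP 7.4.3 states: "The exploratory efficacy analyses will be based on the ITT population, unless otherwise specified".

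SAP 7.3.2 plans a summary of a quantity with the same name, under a different inclusion rule: it "includes subjects who has at least one exposure record during Week 40 to 52".

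On dosing, Protocol 6.4.1.1 has daprodustat subjects start at 4 mg and "remain on the same regimen until the day of Week 4". After that, under Protocol 6.4.1.2, "Dose changes will be made every 4 weeks".

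**The concern.** The label promises doses from the primary efficacy evaluation period. The rule guarantees them only for subjects who have the Week 40, 44 and 48 records. For anyone who stops sooner, the latest three records reach back before Week 40, and the SAP plans no marking of those points. ITT membership needs only a baseline Hgb and one scheduled post-baseline Hgb, so subjects who withdraw early are eligible for the plots.

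The plots are meant to show how the dose reached late in the study relates to patient characteristics. If some points carry doses from months earlier, while the dose was still being titrated, a reader cannot tell which points are late-study doses. Other Week 40 to 52 measures in the SAP do not reach back in this way. Time in target range (SAP 15.6.3) leaves out subjects withdrawn before Week 40. Darbepoetin alfa compliance for the period (SAP 15.6.2) is not calculated when the Week 40 dosing date is missing.

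**Working it through.** **Inputs.** Daprodustat is dispensed every 4 weeks (Protocol Table 10, footnote 2). The daprodustat arm has 135 subjects, and 25% dropout is assumed after the start of treatment (Protocol 4.3). The inclusion rules are those of SAP 15.6.3 and 7.3.2.

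**The plan's own figure.** Dispensing at Day 1, Week 4, ..., Week 48 gives 13 records. The last three are Weeks 40, 44 and 48, as the SAP states for completers.

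**The rule applied to each possible last record** (assuming no skipped records):

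| Last record | Records averaged | Before Week 40 | In the SAP 7.3.2 summary |
|---|---|---|---|
| Day 1 or Week 4 | not plotted (1 or 2 records) | – | no |
| Week 8 | Day 1, Weeks 4 and 8 | 3 of 3 | no |
| Weeks 12 to 36 | that visit and the two before it | 3 of 3 | no |
| Week 40 | Weeks 32, 36, 40 | 2 of 3 | yes |
| Week 44 | Weeks 36, 40, 44 | 1 of 3 | yes |
| Week 48 | Weeks 40, 44, 48 | 0 of 3 | yes |

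The Day 1 record, the only one at the protocol-fixed dose, enters only when the last record is Week 8, as one of three.

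**Number affected.** Expected withdrawals are 0.25 × 135 = 33.75. Timing is not given, so the range comes first:

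- Lower end: every withdrawal has its last record before Week 8 or at Week 48. No plotted point is affected.
- Upper end: every withdrawal has its last record from Week 8 to Week 44. About 34 of 135 points (25%) are affected.

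**Illustration, assuming withdrawals are spread evenly over the 13 intervals and all 135 subjects are in the ITT population.** Each interval has 33.75 / 13 = 2.6 withdrawals.

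- Not plotted (last record Day 1 or Week 4): 2 × 2.6 = 5.2, leaving 135 − 5.2 = 129.8 plotted points.
- Only doses from before Week 40 (last record Weeks 8 to 36, eight visits): 8 × 2.6 = 20.8, or 20.8 / 129.8 = 16%.
- A mix (last record Week 40 or 44): 2 × 2.6 = 5.2.
- At least one dose from before Week 40: 20.8 + 5.2 = 26.0, or 26.0 / 129.8 = 20%.
- Including the Day 1 record: 2.6.

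**The SAP 7.3.2 summary under the same assumption.** Subjects included are 135 − 33.75 + 3 × 2.6 = 109.0. If the latest-three rule also governs this mean, only the 5.2 whose last record is Week 40 or 44 bring in earlier doses, back to Week 32 at most: 5.2 / 109.0 = 5%.

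**The case against.** The best defence is that the variable's name sets the window: the latest three records, and the three-record minimum, would mean records within Weeks 40 to 52. Then only subjects with all of Weeks 40, 44 and 48 are plotted and no earlier dose enters. This reading is possible but weak. Only three dispensing visits fall in the window, so both the reference to the latest three and the qualifier about completers would be redundant. Even on this reading, a subject with one or two in-window records would be in the summary but not in the figures, so the text would still need clarifying.

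It is also fair to say that different inclusion rules for a figure and a table are not in themselves a contradiction. What is unclear is whether the latest-three rule governs the mean in SAP 7.3.2, and which inclusion rule governs the listing.

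A reader might infer more than the documents support, in three ways:

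- That the earliest cases mostly reflect the fixed starting dose. They do not: it is at most one of three records, and absent once the last record is Week 12 or later.
- That the summary table also mixes in early-titration doses. SAP 7.3.2 rules that out for anyone without a record in Weeks 40 to 52.
- That the values are pulled toward the starting dose. No direction is shown. When the last record is Week 8, the algorithm allows three-record means from about 1.3 mg (4, 0, 0) to 6.0 mg (4, 6, 8). SAP 15.6.3 plans individual points only for these figures, so they contain no fitted estimate to bias.

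The defence is right that the stakes are modest. Dose by visit, dose at the final visit and subject profiles are reported separately.

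**Conclusion.** The point holds for the scatter plots. As written, SAP 15.6.3 puts doses from before Week 40 under a Week 40 to 52 label for any plotted subject whose last record is earlier than Week 48.

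The figure of about 34 of 135 is a ceiling and should not be read as an estimate. The 26 of 130 rests on evenly spread withdrawals, the protocol's 25% dropout, no skipped records and full ITT membership. For the SAP 7.3.2 summary the exposure is small and depends on whether the latest-three rule applies there.

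Only exploratory daprodustat figures and a descriptive dose summary are affected. No primary, principal secondary or safety result uses this quantity.

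**What to change.** In SAP 15.6.3, define the daprodustat mean dose for Weeks 40 to 52 as the arithmetic mean of actual doses at scheduled Weeks 40, 44 and 48 only. Apply one inclusion rule, that of SAP 7.3.2 (at least one such record), to the figures, the summary and the listing, and refer to this definition from SAP 7.3.2. No dose from before Week 40 can then enter.

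The cost is about one sentence of SAP text. Under even timing, about 21 points leave the plots (129.8 − 109.0 = 20.8). About 5 of those that remain would rest on one or two records instead of three, and showing the number of records in the listing would make that visible.
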